Appendix 2: Definition and Determination of Outcomes

A2.1 Approach to ascertainment and verification of outcomes

Outcomes are assessed locally and will not be centrally adjudicated in this pragmatic trial platform, except as specified in the arm-specific appendix. Outcomes should be assessed by a local investigator or other qualified study team member who is blinded to treatment assignment, using the definitions below.

A2.2 Outcome definitions

21 Day Organ-Support Free-Days (OSFD)

Defined as the number of days that a patient is alive and free of organ support through 21 days after trial entry. Organ support is defined by receipt of invasive or non-invasive mechanical ventilation, high flow nasal oxygen, vasopressor therapy, ECMO support. If the patient dies at any time (through 90 days) during the index hospital stay, they are assigned the worst possible score of -1.

- Non-invasive mechanical ventilation is defined as BIPAP or CPAP when used for acute respiratory support (the use of BIPAP or CPAP at night or when sleeping for sleep apnea is not considered organ support).
- High Flow Nasal Cannula Oxygen is defined as delivery of oxygen through a system that typically delivers oxygen at 20 to 60 liters per minute with a titratable FiO₂.
- Invasive mechanical ventilation is defined as positive pressure ventilation through endotracheal tube or tracheostomy.
- Vasopressor support includes infusion of any vasopressor or inotropic medication.
- Any patient dying in the acute hospital stay (up to day 90) are assigned 21 Day Organ-Support Free Days of -1.
- If there is intervening time in which a patient is free of organ support but goes back on organ support the intervening time does not count toward the organ support free days endpoint. Only time before organ support and after the last use of organ support are counted as “free days.”
- If a patient was discharged alive without mechanical ventilation prior to Day 21, the patient is assumed to be free of organ support after hospital discharge for the remainder of the 21 days.
- If a patient was discharged alive on mechanical ventilation prior to Day 21, a call to the discharge facility is needed to confirm ventilation status on Day 21 and the last day on mechanical ventilation.

Primary Endpoint

Days free of organ support within 21 days after randomization. Organ support free days (OSFD) is defined as days in which patient is not on invasive or non-invasive mechanical ventilation, high flow nasal oxygen, or vasopressor therapy or ECMO support. If the patient dies at any time (including beyond 21 days) during the index hospital stay, they are assigned the worst possible score of -1.

To be specific about which organ support was affected, secondary outcomes include: ventilator free days, vasopressor free day, and additionally renal replacement therapy free days.

Justification for use of OSFD:

- Pragmatic
- Can be calculated from WHO ordinal scores
- Incorporates clinically important need for organ support but also duration of organ support
- No additional data collection is necessary to calculate secondary outcomes of ventilator free days, renal replacement free days, and vasopressor free days to understand which organ support was most impacted
- Incorporates mortality as the worst possible outcome

Secondary Endpoints**Days free of organ support or RRT during index hospitalization**

Defined as the number of days that a patient is alive and free of cardiovascular and respiratory organ support and free of renal replacement therapy, during the index hospitalization through 28 days after trial entry. Organ support is defined by receipt of invasive or non-invasive mechanical ventilation, high flow nasal oxygen, vasopressor therapy, ECMO support. If the patient dies at any time (through 90 days) during the index hospital stay, they are assigned the worst possible score of -1.

Deep vein thrombosis

Deep vein thrombosis will be diagnosed by venous ultrasound or point-of-care ultrasound (POCUS) or other imaging modality and documented in a note, and performed for clinical indications. A positive ultrasound test is defined by a noncompressible or partially noncompressible venous segment and should be reported. Thrombosis may involve the cerebral venous sinus or any venous bed, including the upper extremities. Routine screening for deep vein thrombosis is not recommended. If deep vein thrombosis is diagnosed and treated without imaging due to imaging availability concerns or risk of exposure to SARS CoV-2, this will be classified as probable deep vein thrombosis. Later imaging is preferable in these cases when possible.

Pulmonary embolism

Pulmonary embolism will be confirmed by chest CT with PE protocol, pulmonary angiography or ventilation-perfusion scan. Events may also be defined without this imaging by the care team, as evidenced by, for example, "clot in transit" on echocardiogram. If PE is diagnosed and treated without imaging due to imaging availability concerns or risk of exposure to SARS CoV-2, this will be classified as probable PE. Later imaging is preferable in these cases when possible.

Stroke/ Peripheral Arterial Systemic Thromboembolism

Stroke or systemic embolism as diagnosed by imaging (i.e., head CT, lower extremity CT angiogram) or deemed "highly-likely" by the provider based on physical examination (i.e., acute hemiplegia thought to be due to stroke, acute distal lower extremity hypoperfusion). Systemic thromboembolism may involve the retinal artery, spinal cord or other vascular beds. Classification of ischemic vs. other etiologies is based on neuroimaging. Venous sinus thrombosis will be included in the category of vascular occlusion/ischemic stroke on the venous side. Primary CNS hemorrhage: intracerebral hemorrhage, subarachnoid hemorrhage, subdural hematoma, and rarely epidural hematoma or spinal hematoma. Secondary hemorrhagic stroke: blood associated with an ischemic infarct.

ICU Level of care disease state (severe illness)

Defined as receipt of cardiovascular or respiratory organ support as defined in the 21-day organ support free days. ICU level of care is defined as being on invasive or non-invasive mechanical ventilation, high flow nasal oxygen, or vasopressor therapy or ECMO support.

Myocardial infarction

Myocardial infarction is defined according to the universal definition of MI, which excludes myocardial injury e.g., isolated elevation of cardiac troponin. MI must include rise and fall of cardiac troponin above the 99th percentile with at least one of the following: symptoms of acute ischemia, ECG changes consistent with ischemia, new/presumed new wall-motion abnormalities or other imaging evidence of MI, abnormal coronary angiography (e.g. identification of a coronary thrombus).

Acute Kidney Injury

Acute kidney injury after enrollment is defined by KDIGO criteria for Acute Kidney Injury in the setting of not meeting these criteria upon enrollment:

Modified Stages:

- Stage 2: Serum Cr 2.0–2.9 times baseline
- Stage 3: Serum Cr \geq 3.0 times baseline, OR Increase in serum creatinine to \geq 4.0mg/dl, OR Initiation of renal replacement therapy

Renal Replacement Therapy (RRT)

This refers to initiation of RRT during the index hospitalization, such as hemodialysis, peritoneal dialysis or continuous venovenous hemofiltration.

WHO ordinal scale for clinical improvement (https://www.who.int/blueprint/priority-diseases/key-action/COVID-19_Treatment_Trial_Design_Master_Protocol_synopsis_Final_18022020.pdf)

Patient State	Score	Descriptor
Uninfected	0	No clinical or virological evidence of infection
Ambulatory	1	No limitation of activities
	2	Symptomatic: Limitation of activities
Hospitalized: Mild disease	3	Hospitalized; no oxygen therapy
	4	Hospitalized; oxygen by mask or nasal prongs
Hospitalized: Severe disease	5	Non-invasive ventilation or high-flow oxygen
	6	Intubation & Mechanical ventilation
	7	Ventilation and additional organ support – pressors, RRT, ECMO
Death	8	Death

Version: 1.2, Date: 19OCT2021

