4.2 Study Endpoints

4.2.1 Primary Study Endpoint

21 Day Organ-Support free-days. The primary endpoint is the number of days that a patient is alive and free of organ support through 21 days after trial entry. Organ support is defined by receipt of invasive or non-invasive mechanical ventilation, high flow nasal oxygen, vasopressor therapy, or ECMO support. If the patient dies at any time during the index hospital stay through 90 days, they are assigned the worst possible score of -1.

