7.1 Study Schedule

Activity	Screening/ Enrollment	Hospital Duration	28 days and/or hospital discharge***	90-days post randomization and longer term follow-up
Eligibility				
Consent	X			
Demographic and Medical History	X			
Assessment of Inclusion/Exclusion criteria	X			
Self-reported race/ethnicity and gender	X			
Study Drug Administration				
Randomization	X			
Study treatment	X	X		
Study Procedures				
Height	X			
Weight	X			
Vital signs	X			
Concomitant medications	X	X		
WHO ordinal assessment	X	X	X	X
Quality of Life and Functional Status [#]	X			X
Outcomes Assessment [#]		X	X	X
SOC Laboratory Assessments				
Chemistry panel	X	X	X	
Hematology panel	X	X		
D-dimer*	X			
Blood Group**	X			

See arm-specific appendices for additional measures

*D-dimer is strongly recommended for measurement in all participants as close to the time of randomization as feasible.

**Blood group will come from hospital record or self-report if available. Biospecimens see appendix 4.

***Assessments indicated in the table above will be ascertained at discharge, or at 28 days, whichever comes first. Participants must be followed for vital status until discharged from the hospital or another care facility (if transferred on organ support) up to 90 days. To maximize retention, participants will be contacted intermittently post-discharge and that contact will be recorded in the EDC.

#Participants may be assessed for functional status and quality of life that reflects baseline status pre-COVID illness and functional and vital status and quality of life at 90 days and longer-term follow-up (Instruments detailed in the manual of operations). Participants may be contacted in the future, including after this study is over to collect information about their health status (e.g. quality of life, functional and vital status) and ascertain their interest in other studies about COVID-19.

Laboratory Procedures/Evaluations

See arm-specific appendices.

All analyses will be performed on SOC labs and procedures done for usual care. The standard operating procedures for samples to be collected for research purposes are included as Appendix 5. All research samples will be timed with clinical lab draws to limit provider exposure. Collection of research samples as outlined in Appendix 5 is strongly encouraged where safe and feasible.

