7.1.1 Visit 1 and Hospitalization Visits (see arm-specific appendices for details)

Visit 1 (Screening and Randomization)

1. Informed consent obtained
2. Assessment of inclusion/exclusion criteria assessed
3. Screening, consisting of reviewing participant medical history and information in their chart such as height, weight, vital signs, and normal clinically performed laboratory assessments, including pregnancy test for all women of childbearing age.
4. If confirmed eligible, following randomization, initiation of treatment with the assigned strategy

Hospitalization Visits

1. Recording of specifics of study treatment and adherence according to assigned arm
2. Laboratory assessments as part of standard of care
3. Daily WHO ordinal assessment
4. Ongoing daily outcomes and safety assessment

7.1.2 28 days and/or Date of Hospital Discharge

1. Recording of outcomes and safety assessments as reported by participant or observed by investigator
2. WHO Ordinal Assessment
3. Recording of vital status and ascertainment of events
4. Recording of participant's adherence to treatment strategy, if patient is in hospital

These assessments will be ascertained at discharge, or at 28 days, whichever comes first. Participants must be followed for vital status until discharged from the hospital or another care facility (if transferred on organ support) up to 90 days.

7.1.3 90 days post-randomization

1. Recording of vital status
2. May include quality of life and functional status assessment

3. May include recording of hospital readmissions

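### The post-discharge rule for the primary endpoint tests only mechanical ventilation, so a patient who leaves on high-flow oxygen, vasopressors or ECMO alone would be scored as support-free to day 21

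*Protocol*

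**What the plan says.** Protocol section 4.2.1 defines the endpoint broadly: "Organ support is defined by receipt of invasive or non-invasive mechanical ventilation, high flow nasal oxygen, vasopressor therapy, or ECMO support". Appendix 2 (A2.2) repeats that list and gives the non-ventilator components their own definitions: "High Flow Nasal Cannula Oxygen is defined as delivery of oxygen through a system that typically delivers oxygen at 20 to 60 liters per minute", and "Vasopressor support includes infusion of any vasopressor or inotropic medication".

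Two later bullets in A2.2 settle the days after discharge, and both turn on ventilation alone:

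- Not ventilated at discharge: if the patient is "discharged alive without mechanical ventilation prior to Day 21, the patient is assumed to be free of organ support after hospital discharge", all remaining days to day 21 count as free.
- Ventilated at discharge: "a call to the discharge facility is needed to confirm ventilation status on Day 21 and the last day on mechanical ventilation".

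Transfer on support is foreseen elsewhere. The footnote to the schedule in section 7.1, and section 7.1.2, state: "Participants must be followed for vital status until discharged from the hospital or another care facility (if transferred on organ support) up to 90 days". They ask for vital status and name no organ-support data.

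The SAP (section 4.3 and section 7, endpoint 1) uses the broad definition, gives no post-discharge rule, and refers to a data dictionary for the detailed calculation. For the mortality endpoint (SAP section 7, endpoint 4), it separates discharges by whether the patient was off organ support, which is the wider test.

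**The concern.** The endpoint counts several kinds of support, but the rule that completes it after discharge checks only one. A patient who leaves on high-flow oxygen, a vasopressor or inotrope, or ECMO, and is not ventilated, falls under the first bullet and is treated as free of all support from that day. The facility call is not triggered. A call made for a ventilated patient would not ask about the other supports either.

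High-flow oxygen is a central component: under Appendix 2 it is enough by itself to place a patient in the severe cohort. The error always raises the score, and it falls on patients who are still on support. The score drives the superiority and futility triggers in SAP section 4.4, so the rule should match the definition. The question is how far a mismatch could move the odds ratio.

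**Working it through.** The plan gives no figure tied to this rule, so there is nothing of its own to reproduce. The check has three steps.

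**1. Coverage of the two bullets**

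| Support when leaving before day 21 | Organ support by definition? | Rule that applies | Support after leaving recorded? |
|---|---|---|---|
| Invasive or non-invasive ventilation | Yes | Second bullet: call | Ventilation only |
| High-flow oxygen, not ventilated | Yes | First bullet: assumed free | No |
| Vasopressor or inotrope, not ventilated | Yes | First bullet: assumed free | No |
| ECMO, not ventilated | Yes | First bullet: assumed free | No |

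A2.2 treats BIPAP and CPAP for acute support as non-invasive mechanical ventilation, so the gap is the last three rows. Days on support before discharge are still counted correctly.

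**2. One patient**

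Take a patient on support from day 0 who leaves on day d and whose true last day of support is L (capped at 21).

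- Score by the rule: 21 − d
- Score by the definition: 21 − L
- Overscoring: L − d

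Examples:

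- High-flow oxygen from day 0, transferred on day 3 still on it, intubated on day 4, ventilated and alive past day 21: rule 21 − 3 = 18, definition 21 − 21 = 0.
- Leaves on day 10, support to day 21: 11 against 0.
- Leaves on day 10, support to day 13: 11 against 8.

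**3. Effect on the odds ratio (all inputs assumed)**

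The documents give neither the outcome distribution nor the rate of leaving on these supports. I therefore assumed control distributions and set the treated arm by logit P(Y ≤ y, treated) = logit P(Y ≤ y, control) − log(OR). I then moved a stated percentage of all patients in an arm from 0 to a landing score and fitted a proportional-odds model by maximum likelihood to the expected cell probabilities.

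Distribution A has 30% at −1, 10% at 0 and the remaining 60% spread evenly over 1 to 21. Distribution B has 33% at −1, 12% at 0, 45% spread evenly over 1 to 20, and 10% at 21.

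| Distribution, landing score | Moved, control / treated | True OR | Fitted OR |
|---|---|---|---|
| A, 18 | 2.5% / 2.5% | 1.40 | 1.392 |
| A, 18 | 5% / 5% | 1.40 | 1.384 |
| A, 18 | 2.5% / 2.5% | 1.20 | 1.196 |
| A, 18 | 5% / 5% | 1.20 | 1.192 |
| A, 11 | 5% / 5% | 1.20 | 1.200 |
| A, 7 | 5% / 5% | 1.20 | 1.202 |
| B, 11 | 5% / 5% | 1.20 | 1.199 |
| A, 18 | 1% / 2% | 1.00 | 1.03 |
| A, 18 | 2% / 4% | 1.00 | 1.07 |
| B, 11 | 1% / 3% | 1.00 | 1.04 |
| B, 11 | 3% / 1% | 1.00 | 0.96 |

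Equal movement changes the odds ratio by less than 0.02 in every row, and its direction depends on the landing score. Unequal movement shifts the odds ratio toward the arm with more misscored patients.

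**The case against.** Four points can be made for the plan.

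- **The number affected is probably small.** Few patients leave hospital on these supports without ventilation, and transfer to another facility is the realistic route. This stands. It limits the size of the problem but does not close the gap.
- **A difference between arms is speculative.** Randomization is stratified by site (Protocol section 2.2), the SAP model includes site (section 12.1), and A2.1 asks for assessors blinded to assignment. These largely balance transfer practice at site level. Treatment is open label, however, so a difference within sites cannot be excluded. The unequal rows above show sensitivity and are not a forecast.
- **Discharge may not mean transfer.** The follow-up text and the SAP mortality endpoint treat transfer on support separately. But the second A2.2 bullet itself speaks of a facility to be called, so its discharges include transfers. The text is at best ambiguous.
- **The data dictionary may already be right.** It may be, and it was not available. A2.1 nevertheless tells assessors to use the definitions in A2.2, so that wording needs correcting in any case. The statement in Appendix 2 that the endpoint can be derived from WHO scores does not help, because daily scoring is an in-hospital activity (section 7.1.1).

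A reader might also infer that the rule credits free days after a death following discharge. The text does not support this: the bullet assumes freedom from support, not survival, and the governing definition still requires the patient to be alive.

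**Conclusion.** The two discharge bullets are narrower than the endpoint they complete, and nothing in the Protocol or SAP corrects this. Followed literally, they overscore an affected patient by the number of days of support after discharge, up to 18 in the example. This should be fixed, but it does not show that the trial's primary result is compromised.

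Two stronger readings are tempting. One is that the primary scores are in fact wrong. That cannot be established without the data dictionary and the number of such patients. The other is that misclassification in both arms generally dilutes the treatment effect. The calculation does not support this: with 5% moved in each arm, the change is negligible for a landing score of 11 and very slightly upward for 7. Only an imbalance between arms matters. With no drug effect, the assumed imbalances give odds ratios from 0.96 to 1.07, to be read beside the SAP's futility margin of 1.20. These figures rest on assumed distributions, rates and landing scores.

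**What to change.** In both A2.2 discharge bullets, replace mechanical ventilation with organ support as defined above in the same section. Have the existing facility call record the last day of any component (invasive or non-invasive ventilation, high-flow oxygen, vasopressors or inotropes, ECMO) through day 21. Put the same rule in the data dictionary cited in SAP section 4.3.

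The cost is a change of wording, a few more calls for patients who leave on non-ventilator support, and less favourable scores for those patients. No new visit is needed. The calls would also show how many patients are affected, which the documents leave unknown.

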4.2.2 Secondary Endpoints

- Categorization of the primary endpoint into a three-level ordinal outcome (Death, invasive mechanical ventilation without death, neither invasive mechanical ventilation nor death)
- Categorization of the primary endpoint into a three-level ordinal outcome (Death, organ support (any respiratory or cardiovascular) without death, neither organ support nor death) (for moderate illness severity at enrollment)
- Days free of death and respiratory and cardiovascular organ support and renal replacement therapy (RRT) during Index Hospitalization through Day 28. If the patient dies at any time during the index hospital stay through 90 days, they are assigned the worst possible score of -1.
- A composite endpoint of death, pulmonary embolism, systemic arterial thromboembolism, myocardial infarction, or ischemic stroke during hospitalization or at 28 days after enrollment (whichever is earlier) – “major thrombotic events or death”
- 28 Day Hospital free days (non-ICU level patients)
- 28 Day Ventilator-Free Days (ICU level patients)
- 28 Day Vasopressor-Free Days (ICU level patients)
- 28 Day Renal Replacement Free Days
- Hospital readmission within 28 days
- Acute kidney injury
- Deep vein thrombosis
- Pulmonary embolism
- Systemic arterial thrombosis or embolism
- Myocardial infarction
- Ischemic stroke
- Renal replacement therapy
- Use of extracorporeal membrane oxygenation (ECMO) support
- Mechanical circuit (dialysis or ECMO) thrombosis
- WHO ordinal scale (peak scale over 28 days, scale at 14 days, and proportion with improvement by at least 2 categories compared to enrollment, at 28 days)
- All-cause mortality at 28 days
- All-cause mortality during initial hospitalization (includes death after 28 days)
- All-cause mortality at 90 days

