**7. Renal replacement-free days to day 28**

- Restricted to patients not on Renal Replacement Therapy at baseline
- An ordinal outcome of the number of days free of renal replacement therapy in the hospital. Death is considered a 0 (consistent ACTIV-4A protocol 1.0).
- Compute renal replacement-free days based on integer days on which renal replacement therapy was not received at any time
- Renal replacement-free days will be computed based on the duration of time from the initiation of renal replacement therapy to the final cessation of renal replacement therapy during the 28-day period; intervening days on which patients are not on renal replacement therapy will be ignored

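### The 28-day days-free-of-organ-support-or-RRT endpoint counts only in-hospital days as written, so a shorter support-free stay lowers the score

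*Protocol*

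**What the plan says.** Protocol section 4.2.2 lists the endpoint as "Days free of death and respiratory and cardiovascular organ support and renal replacement therapy (RRT) during Index Hospitalization through Day 28", and the Master Protocol Summary uses the same window. Appendix 2, A2.2, heads it "Days free of organ support or RRT during index hospitalization" and defines it as a count of days alive, off organ support and "free of renal replacement therapy, during the index hospitalization through 28 days after trial entry". Death is the bottom of the scale: "If the patient dies at any time (through 90 days) during the index hospital stay, they are assigned the worst possible score of -1". Higher scores are therefore better.

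The primary endpoint is set up differently. Appendix 2 describes the OSFD this way: "Defined as the number of days that a patient is alive and free of organ support through 21 days after trial entry". Hospital stay does not limit that window. For patients discharged alive without mechanical ventilation before day 21, it adds that "the patient is assumed to be free of organ support after hospital discharge for the remainder of the 21 days". It also requires a call to the discharge facility for those who leave on mechanical ventilation. Neither rule is extended to 28 days or to RRT.

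SAP section 7 lists 35 endpoints, and this composite is not among them. The nearest is item 7, renal replacement-free days to day 28, described as "An ordinal outcome of the number of days free of renal replacement therapy in the hospital". Its computation bullets then work from the start to the final cessation of RRT within the 28-day period.

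**The concern.** A count of good days that stops at discharge penalizes leaving hospital. For a survivor who never needs support or RRT, every day alive in hospital counts and every day at home does not, so the score is simply length of stay up to 28. The ordering then conflicts with the purpose of the scale, and with the protocol's own 28-day hospital-free days, which rise with early discharge.

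The moderate cohort is the most exposed. Its patients are off organ support at randomization by definition, and Arms E and F enrol them. If treatment helps such patients go home sooner, this endpoint would tend to move against it. Readers would then see a secondary result that disagrees with the primary for a reason that lies in the scoring.

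**Working it through.** The documents give no sample size, effect or event rate for this endpoint, so there is no planned figure to reproduce. The check scores example patients, then simulates.

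**Two scoring rules**

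- Rule A (as written): min(length of stay, 28) − days on support or RRT; in-hospital death = −1.
- Rule B (OSFD discharge rule carried to day 28): 28 − days on support or RRT; in-hospital death = −1.

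**Single patients** (continuous support, no assumed distributions)

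| Patient | Rule A | Rule B |
|---|---|---|
| Never supported, home day 5 | 5 | 28 |
| Never supported, home day 6 | 6 | 28 |
| Never supported, home day 10 | 10 | 28 |
| Supported days 1–10, home day 14 | 14 − 10 = 4 | 28 − 10 = 18 |
| Supported 7 days, in hospital to day 28 | 28 − 7 = 21 | 21 |
| Supported days 1–10, in hospital to day 28 | 28 − 10 = 18 | 18 |
| Supported days 1–20, in hospital to day 28 | 28 − 20 = 8 | 8 |
| In-hospital death | −1 | −1 |

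Under rule A, the patient home on day 5 without support (5) ranks below the patient supported for 20 days and still in hospital (8). Rule B puts them at 28 and 8.

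**Simulation 1: only the stay changes.** All inputs are assumptions: 200,000 patients per arm, lognormal stay (sigma 0.6), 15% supported with lognormal duration (median 6 days), and 6% deaths. Support and death are identical in both arms. Win/loss odds are treated-better pairs divided by treated-worse pairs.

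| Median stay, control to treated | Rule A | Rule B |
|---|---|---|
| 6 to 5.5 days | 0.86 | about 1.00 |
| 6 to 5 days | 0.72 | about 1.00 |
| 8 to 7 days | 0.79 | about 1.00 |

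**Simulation 2: other changes allowed.** These inputs are also assumptions: 200,000 per arm, gamma durations with shape 2.

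- Moderate control: 8% deaths, 20% supported, mean support 8 days, mean stay 7 days without support and 6 days after it.
- Severe control: 25% deaths, all supported, mean support 12 days, mean stay after support 7 days.

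The measure is the probability that a treated patient scores better, plus half of ties; below 0.5 looks like harm.

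| Change in treated arm | Rule A | Rule B |
|---|---|---|
| Moderate: stay −1 day only | 0.450 | 0.499 |
| Moderate: stay −2 days only | 0.393 | 0.499 |
| Moderate: stay −1 day, support 20% to 16%, death 8% to 6% | 0.461 | 0.526 |
| Severe: support −2 days, later stay unchanged | 0.515 | 0.539 |
| Severe: support −2 days, later stay −1 day | 0.486 | 0.537 |
| Severe: as above, plus death 25% to 22% | 0.501 | 0.554 |

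The third row is a benefit on all three components that rule A shows as harm. The fourth shows the limit of the problem: when only support shortens, the benefit shrinks but keeps its sign.

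**The case against.** The strongest reply is that the reference to the index hospitalization says where support is ascertained and does not limit which days are counted. In section 4.2.2 the phrase "renal replacement therapy (RRT) during Index Hospitalization through Day 28" follows the list of events and can be read that way. Appendix 2 defines RRT as started during the index stay, the sibling OSFD credits days after discharge, and hospital-free days reward early discharge. This is a plausible intention. It is not written for this endpoint, though, and the Appendix 2 sentence ties the window to the count of days. Outcomes are assessed locally against those definitions, so two people could score the same patient differently. The OSFD rule cannot simply be borrowed either: it turns on mechanical ventilation and is silent on a patient discharged on RRT.

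A reader might also infer three stronger points that the documents do not support.

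- **Any drug that shortens the stay will look harmful.** Reversal needs the support-free part of the stay to shorten. Otherwise the benefit is diluted, and a mortality gain can offset the loss.
- **SAP item 7 has the same reversed scale.** Its computation uses RRT duration within the 28-day period, so a patient never on RRT would naturally score 28. Its wording is ambiguous, not reversed.
- **A misleading odds ratio is already planned on a leading secondary endpoint.** The SAP's key secondary endpoints are in-hospital mortality and major thrombotic events or death. It specifies no model for this composite.

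**Conclusion.** The concern holds for the definition as written. The protocol states the window consistently in three places, and that window ranks some survivors in the wrong order; the single-patient results rest only on the text. The size of any distortion between arms rests on assumed distributions. With support and death held equal and a median stay shorter by half a day to one day, win/loss odds fall to about 0.72–0.86 where they should be about 1.00. The effect is greatest in moderate patients; among severe patients it ranges from dilution to a small reversal, depending on whether the stay after support also shortens. The primary OSFD, its superiority and futility triggers, and the SAP's key secondary endpoints are not affected. It should be corrected before this endpoint is analysed.

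**What to change.** - Define the endpoint as days alive and free of organ support and RRT from randomization through day 28, keeping −1 for in-hospital death through day 90.
- Count patients discharged alive without organ support or RRT as free through day 28.
- For those discharged on either, extend the existing facility call to day 28 and to RRT.
- Remove the index hospitalization as a limit on the counting window in the Master Protocol Summary, section 4.2.2 and Appendix 2 (heading and definition).
- Add the endpoint, its scoring and its model to the SAP.
- In SAP section 7, item 7, state that the reference to the hospital does not limit the days counted.

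The cost is mostly wording. The one new data need is day-28 status, including RRT, for patients discharged on support or RRT. This is a small addition, because the protocol already calls facilities about ventilated patients discharged before day 21.
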